11.5.1.2 Measures of alcohol use

Alcohol consumption will be recorded by the patients using TLFB. The number of standard drinks will be recorded daily.

The proportion of days of alcohol consumption during the study treatment period will be compared between groups using an ANCOVA model with treatment as factor and past alcohol consumption as covariate.

The longitudinal profiles (daily number of drinks, weekly and monthly mean number of drinks) will be explored.

11.5.2 Safety

Vital signs

All vital signs data will be listed by treatment group, subject, and visit/time and if ranges are available abnormalities (and relevant orthostatic changes) will be flagged. Summary statistics will be provided by treatment and visit/time.

ECG evaluations

All ECG data will be listed by treatment group, subject and visit/time, abnormalities will be flagged. Summary statistics will be provided by treatment and visit/time.

Clinical laboratory evaluations

All laboratory data will be listed by treatment group, subject, and visit/time and if normal ranges are available abnormalities will be flagged. Summary statistics will be provided by treatment and visit/time.

Adverse events

All information obtained on adverse events will be displayed by treatment group and subject.

The number and percentage of subjects with adverse events will be tabulated by body system and preferred term with a breakdown by treatment. A subject with multiple adverse events within a body system is only counted once towards the total of this body system.

Other safety evaluations

Columbia Suicide Severity Rating Scale (C-SSRS). The C-SSRS data will be listed by treatment group, subject and visit.

11.5.3 Pharmacokinetics

Analysis will be performed under PK analysis set.

AFQ056 plasma concentration data will be listed by treatment, subject, and visit/sampling time point.

Commercially Confidential Information

Conventional PK parameters will not be calculated due to the limited sampling schedule. However, plasma concentrations will be listed at pre-dose and $2\pm I$ hour sampling window post morning dose and summary statistics for concentrations will be provided for plasma. The data will be part of the over-all Population PK model.

Commercially Confidential Information

11.5.4 Pharmacokinetic / pharmacodynamics interactions

Not applicable.

11.5.5 Other assessments

Not applicable.

11.6 Analysis of exploratory variables (if applicable)

Commercially Confidential Information

11.7 Sample size calculation

A sample size of approximately 60 patients (30 patients on AFQ056 and 30 patients on placebo) was determined, assuming a SD of 32% ([Nuijten et al 2016](#)) for the proportion of cocaine use days. Patients who are withdrawn from the study for reasons other than safety may be replaced, if the drop-out rate is higher than anticipated (20 % higher).

Commercially Confidential Information

Commercially Confidential Information

11.8 Power for analysis of key secondary variables

Not applicable.

11.9 Interim analyses

Commercially Confidential Information

12 Ethical considerations

12.1 Regulatory and ethical compliance

This clinical study was designed and shall be implemented, executed and reported in accordance with the ICH Harmonized Tripartite Guidelines for Good Clinical Practice, with applicable local regulations (including European Directive 2001/20/EC, US Code of Federal Regulations Title 21, and Japanese Ministry of Health, Labor, and Welfare), and with the ethical principles laid down in the Declaration of Helsinki.

12.2 Responsibilities of the investigator and IRB/IEC

Before initiating a trial, the investigator/institution must obtain approval/favorable opinion from the Institutional Review Board/Independent Ethics Committee (IRB/IEC) for the trial protocol, written informed consent form, consent form updates, subject recruitment procedures (e.g. advertisements) and any other written information to be provided to subjects. Prior to study start, the investigator is required to sign a protocol signature page confirming his/her agreement to conduct the study in accordance with these documents and all of the instructions and procedures found in this protocol and to give access to all relevant data and records to Novartis monitors, auditors, Novartis Quality Assurance representatives, designated agents of Novartis, IRBs/IECs, and regulatory authorities as required. If an inspection of the clinical site is requested by a regulatory authority, the investigator must inform Novartis immediately that this request has been made.

For multi-center trials, a Coordinating Investigator will be selected by Novartis by the time of Last Patient Last Visit to be a reviewer and signatory for the clinical study report.

12.3 Publication of study protocol and results

The key design elements of this protocol will be posted in a publicly accessible database such as clinicaltrials.gov. In addition, upon study completion and finalization of the study report the results of this trial will be either submitted for publication and/or posted in a publicly accessible database of clinical trial results.

12.4 Quality Control and Quality Assurance

Novartis maintains a robust Quality Management (QM) system that includes all activities involved in quality assurance and quality control, including the assignment of roles and responsibilities, the reporting of results, and the documentation of actions and escalation of issues identified during the review of quality metrics, incidents, audits and inspections.

Audits of investigator sites, vendors, and Novartis systems are performed or overseen by Novartis Pharma Auditing and Compliance Quality Assurance (or CRO working on behalf of Novartis), a group independent from those involved in conducting, monitoring or performing quality control of the clinical trial. The clinical audit process uses a knowledge/risk based approach.

Audits are conducted to assess GCP compliance with global and local regulatory requirements, protocols and internal SOPs, and are performed according to written Novartis processes.

13 Protocol adherence

This protocol defines the study objectives, the study procedures and the data to be collected on study participants. Additional assessments required to ensure safety of subjects should be administered as deemed necessary on a case by case basis. Under no circumstances is an investigator allowed to collect additional data or conduct any additional procedures for any research related purpose involving any investigational drugs under the protocol.

Investigators ascertain they will apply due diligence to avoid protocol deviations. If an investigator feels a protocol deviation would improve the conduct of the study this must be considered a protocol amendment, and unless such an amendment is agreed upon by Novartis and approved by the IRB/IEC and health authorities, where required, it cannot be implemented.

The United Nations Office on Drugs and Crime (UNODC) (2016) UNODC-WHO International Standards for the Treatment of Drug Use Disorders.

15 Appendix 1: Liver Event Definitions and Follow-up Requirements

Table 15-1 Liver Event Definitions

Definition	Thresholds
Potential Hy's law cases	
 ALT or AST > 3 × ULN and TBL > 2 × ULN without initial increase in ALP to > 2 × ULN
ALT or AST elevation with coagulopathy	
 ALT or AST > 3 × ULN and INR > 1.5 (in the absence of anticoagulation)
ALT or AST elevation accompanied by symptoms	
 ALT or AST > 3 × ULN accompanied by (general) malaise, fatigue, abdominal pain, nausea, or vomiting, or rash, or eosinophilia
Isolated ALT or AST elevation	
 ALT or AST > 8 × ULN 5 × ULN < ALT/AST ≤ 8 × ULN 3 × ULN < ALT/AST ≤ 5 × ULN
Isolated ALP elevation	
 ALP > 2 × ULN (in the absence of known bone pathology)
Others	
 Any clinical event of jaundice (or equivalent term) Any adverse event potentially indicative of liver toxicity

Table 15-2 Actions required for Liver Events

Criteria	Actions required
Potential Hy's Law case	
ALT or AST elevation with coagulopathy	
 Discontinue the study treatment immediately
ALT or AST elevation accompanied by symptoms	
 Hospitalize, if clinically appropriate Establish causality
Isolated ALT or AST elevation > 8 × ULN	
 Complete CRFs per liver event guidance*
Jaundice	
 If confirmed, consider interruption or discontinuation of study drug
Isolated ALT or AST elevation > 5 to ≤ 8 × ULN	
 If elevation persists for more than 2 weeks, discontinue the study drug Establish causality Complete CRFs per liver event guidance*
Isolated ALT or AST elevation > 3 to ≤ 5 × ULN (patient is asymptomatic)	
 Monitor liver chemistry tests two or three times weekly Repeat liver chemistry tests within 48-72 hours
Isolated ALP elevation	
 If elevation is confirmed, measure fractionated ALP; if >50% is of liver origin, establish hepatic causality Complete CRFs per liver event guidance* Consider study treatment interruption or discontinuation
Any AE potentially indicative of liver toxicity	
 Hospitalize if clinically appropriate Complete CRFs per liver event guidance*

*Liver event guidance for CRF completion is available in the Site Operations Manual

Table 15-3 Exclusion of underlying liver disease

Disease	Assessment
Hepatitis A, B, C, E	
• IgM anti-HAV; HBSAg, IgM anti-HBc, HBV DNA; anti-HCV, HCV RNA, IgM & IgG anti-HEV, HEV RNA
CMV, HSV, EBV infection	
• IgM & IgG anti-CMV, IgM & IgG anti-HSV; IgM & IgG anti-EBV
Autoimmune hepatitis	
• ANA & ASMA titers, total IgM, IgG, IgE, IgA
Alcoholic hepatitis	
• Ethanol history, GGT, MCV, CD-transferrin
Nonalcoholic steatohepatitis	
• Ultrasound or MRI
Hypoxic/ischemic hepatopathy	
• Medical history: acute or chronic CHF, hypotension, hypoxia, hepatic venous occlusion. Ultrasound or MRI.
Biliary tract disease	
• Ultrasound or MRI, ERCP as appropriate.
Wilson disease	
• Caeruloplasmin
Hemochromatosis	
• Ferritin, transferrin
Alpha-1-antitrypsin deficiency	
• Alpha-1-antitrypsin

16 Appendix 2: Specific Renal Alert Criteria and Actions

Table 16-1 Specific Renal Alert Criteria and Actions

Criteria	Action required
Serum creatinine (sCr) increase 25 – 49% compared to baseline	
 Consider causes and possible interventions Follow up within 2-5 days
Serum creatinine increase > 50%	
 Consider causes and possible interventions Repeat assessment within 24-48h if possible Consider drug interruption or discontinuation unless other causes are diagnosed and corrected Consider hospitalization and specialized treatment
Protein-creatinine or albumin-creatinine ratio increase \geq 2-fold	
or	
new onset dipstick proteinuria \geq 1+	
 Consider causes and possible interventions Assess serum albumin & serum protein
or	
Albumin-creatinine ratio (ACR) \geq 30 mg/g or \geq 3 mg/mmol;	
 Repeat assessment to confirm Consider drug interruption or discontinuation unless other causes are diagnosed and corrected
or	
Protein-creatinine ratio (PCR) \geq 150 mg/g or >15 mg/mmol	
New onset glucosuria on urine dipstick (unless related to concomitant treatment, diabetes)	
Assess & document:
 
 Blood glucose (fasting) Serum creatinine Urine albumin-creatinine ratio 
Assess & document:

New hematuria on dipstick	
 Urine sediment microscopy Assess sCr and urine albumin-creatinine ratio Exclude infection, trauma, bleeding from the distal urinary tract/bladder, menstruation Consider bleeding disorder

Additional specialized assessments are available to assess renal function or renal pathology. (Note: In exceptional cases when a nephrologist considers a renal biopsy, it is strongly recommended to make specimen slides available for evaluation by Novartis to potentially identify project-wide patterns of nephrotoxicity.)

Whenever a renal event is identified, a detailed subject history and examination are indicated to identify, document and potentially eliminate risk factors that may have initiated or contributed to the event:

- Blood pressure assessment (after 5 min rest, with an appropriate cuff size)
- Signs and symptoms such as fever, headache, shortness of breath, back or abdominal pain, dysuria, hematuria, dependent or periorbital edema

- Changes in blood pressure, body weight, fluid intake, voiding pattern, or urine output
- Concomitant events or procedures such as trauma, surgical procedures, cardiac or hepatic failure, contrast media or other known nephrotoxin administration, or other potential causes of renal dysfunction, e.g., dehydration, hemorrhage, tumor lysis

Table 16-2 Follow-up of renal events

Action	Follow up
Assess*, document and record in the Case Report Form (CRF) or via electronic data load. Review and record possible contributing factors to the renal event (co-medications, other co-morbid conditions) and additional diagnostic procedures (MRI etc) in the CRF.	
 • Urine dipstick and sediment microscopy • Blood pressure and body weight • Serum creatinine, electrolytes (sodium, potassium, phosphate, calcium), bicarbonate and uric acid • Urine output • Event resolution: (sCr within 10% of baseline or protein-creatinine ratio within 50% of baseline)
Monitor subject regularly (frequency at investigator's discretion) until:	
or
 
 • Event stabilization: sCr level with $\pm 10\%$ variability over last 6 months or protein-creatinine ratio stabilization at a new level with $\pm 50\%$ variability over last 6 months.

* Urine osmolality: in the absence of diuretics or chronic kidney disease this can be a very sensitive metric for integrated kidney function that requires excellent tubular function. A high urinary osmolality in the setting of an increase in sCr will point toward a "pre-renal" cause rather than tubular toxicity.

17 Appendix 3: Drugs affecting CYP3A4

Drugs affecting CYP3A4

This appendix provides a specific list of drugs that should not be co-administered with AFQ056 because of their CYP3A4 inhibiting potency or CYP3A4 inducing potency.

Drugs inhibiting CYP3A4

This list is by no means exhaustive and medical judgment should always prevail. The clinical investigators must refer to the product information of any concomitant medication to ascertain any potential drug interactions. This list is adapted to the patient population and the exclusion criteria.

List of CYP3A4 inhibitors not to be co-administered with AFQ056 in study CAFQ056A2201

- Amiodarone
- Amprenavir
- Aprepitant
- Atazanavir
- Cimetidine
- Clarithromycin
- Diltiazem
- Erythromycin
- Fluconazole
- Fluoroquinolones (e.g. ciprofloxacin)
- Fluvoxamine
- Fosamprenavir
- Gestodene
- Grapefruit juice
- Indinavir
- Itraconazole
- Ketoconazole
- Mibefradil
- Nefazodone
- Nelfinavir
- Ritonavir

- Saquinavir
- Telithromycin
- Verapamil
- Voriconazole

Drugs inducing CYP3A4:

- Barbiturates (e.g. primidone, phenobarbital)
- Carbamazepine
- Efavirenz
- Glucocorticoids (except for topical or inhalation use)
- Phenytoin
- Rifabutin
- Rifampin
- Rifapentin
- St. John's Wort

## **1 Introduction**

### **1.1 Scope of document**

The RAP documents contain detailed information to aid the production of Statistics & Programming input into the Clinical Study Report (CSR) for trial “**CAFQ056X2201**”.

The Statistical analysis plan (SAP) describes the implementation of the statistical analysis planned in the protocol.

### **1.2 Study reference documentation**

This SAP has been developed using Clinical Trial Protocol version v01 dated 15 November 2017.

### **1.3 Study objectives**

#### **1.3.1 Primary objective**

To evaluate treatment effect of 98-day AFQ056 administration in reducing cocaine use.

#### **1.3.2 Secondary objectives**

- To assess the effects of 98-day AFQ056 administration versus placebo on:
  - a) other measures of cocaine use
  - b) alcohol use
- To assess the safety and tolerability of multiple bid oral doses of AFQ056.
- To evaluate the pharmacokinetics of AFQ056.

#### **1.3.3 Exploratory objectives**

[figure not shown]
Commercially Confidential Information

### **1.4 Study design and treatment**

This is a randomized, subject and investigator blinded, parallel group, placebo-controlled study in approximately 60 patients with cocaine use disorder. The study consists of: about 17-day screening period followed by a 12-day baseline; a 98-day out-patient treatment period (14-day up-titration dose regimen followed by 84-day maintenance dose) and finally an end of study visit evaluation approximately 14-days after the last study drug administration. The total

duration for each patient in the study is up to approximately 20-weeks including screening and baseline. The study design is summarized in Figure 1.4-1 below.

**Figure 1.4-1 Overall study scheme**

Following baseline, on Day 1, approximately 60 eligible patients will be randomly assigned in a 1:1 ratio to either AFQ056 or placebo.

- Group A – AFQ056: up-titration regimen for the first 2 weeks (14 days): 50 mg bid from Day 1 to Day 7, 100 mg bid from Day 8 to Day 14, followed by dosing at 200 mg bid for 84-days.
- Group B: matching placebo.

## 2 First interpretable results (FIR)

First interpretable results (FIR) will be provided for this trial.

Commercially Confidential Information

## 3 Interim analyses

Commercially Confidential Information

## 4 Statistical methods: Analysis sets

For subjects for which the actual treatment received does not match the randomized treatment the treatment actually received will be used for the analysis.

The randomized set will include all subjects randomized.

The safety analysis set will include all subjects that received any study drug.

The PK analysis set will include all subjects with at least one available valid (i.e. not flagged for exclusion) PK concentration measurement, who received any study drug and experienced no protocol deviations with relevant impact on PK data.

The PD analysis set will include all subjects with any available PD data, who received any study drug for at least 14 days in the treatment period and experienced no protocol deviations with relevant impact on PD data.

The Full analysis set (FAS) will include all subjects with any available PD data who received at least any study drug.

The analysis sets and protocol deviation codes are related as follows:

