11.1 Analysis sets

For all analysis sets, subjects will be analyzed according to the study treatment received.

The safety analysis set will include all subjects that received any study drug.

The PK analysis set will include all subjects with at least one available valid (i.e. not flagged for exclusion) PK concentration measurement, who received any study drug and with no protocol deviations that impact on PK data.

The PD analysis set will include all subjects with available PD data and no protocol deviations with relevant impact on PD data.

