**Table 4-1 Protocol deviation codes and analysis sets**

Category Deviation code	Text description of deviation	Data exclusion
Subjects are excluded from PK analysis in case of these PDs:		
TRT02	Subject was randomized but did not take any dose of study treatment	Exclude subject from PK analysis set Subject will be counted in randomized set, but excluded from safety, PD and PK analysis sets
TRT05	Bad compliance to study treatment	Exclude subject from PD and PK analysis sets
Subjects are excluded from PD analysis in case of these PDs:		
TRT02	Subject was randomized but did not take any dose of study treatment	Exclude subject from PD analysis set Subject will be counted in randomized set, but excluded from safety, PD and PK analysis sets
TRT05	Bad compliance to study treatment	Exclude subject from PD and PK analysis sets
Subjects are excluded from PK and PD analysis in case of these PDs:		
		Exclude subject from PK and PD analysis sets

Category Deviation code	Text description of deviation	Data exclusion
TRT02	Subject was randomized but did not take any dose of study treatment	Subject will be counted in randomized set, but excluded from safety, PD and PK analysis sets
TRT05	Bad compliance to study treatment	Exclude subject from PD and PK analysis sets
Subjects are excluded from Safety analysis in case of these PDs:		Exclude subject from Safety analysis set
TRT02	Subject was randomized but did not take any dose of study treatment	Subject will be counted in randomized set, but excluded from safety, PD and PK analysis sets
Subjects are analyzed according to treatment actually received		
TRT04	Wrong treatment arm medication given to the subject by mistake of pharmacist – not according to treatment randomized.	Subject will be analyzed according to treatment actually received (ie the other trt group than randomized)

If updates to this table are needed, an amendment to the SAP needs to be implemented prior to DBL.

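### The PD set is selected on events after randomisation and every set is analysed as treated; confirm the FAS, by randomised arm, for the efficacy comparisons

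*SAP*

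**What the plan says.** **PD set.** SAP section 4 reads: "The PD analysis set will include all subjects with any available PD data, who received any study drug for at least 14 days", and adds that there must be no deviation affecting PD data. Protocol 11.1 has no exposure minimum: "The PD analysis set will include all subjects with available PD data and no protocol deviations with relevant impact on PD data". Fourteen days is the length of up-titration in protocol 6.2.

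**Compliance.** In SAP Table 4-1, code TRT05, "Bad compliance to study treatment", takes the whole patient out of the PD and PK sets. The visible text gives no cut-off. The table has no code for the 14-day rule.

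**Treatment assignment.** Protocol 11.1: "For all analysis sets, subjects will be analyzed according to the study treatment received". SAP section 4: "For subjects for which the actual treatment received does not match the randomized treatment the treatment actually received will be used for the analysis". Neither sentence is limited to safety. Table 4-1 repeats the rule under TRT04, the code for medication of the wrong arm.

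**FAS.** Only the SAP defines one: "The Full analysis set (FAS) will include all subjects with any available PD data who received at least any study drug". It carries neither the 14-day nor the compliance rule, but the as-treated sentence covers it too. A randomised set is also defined; no visible analysis uses it.

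**Set for the primary comparison.** Not visible. Protocol 11.4.2 and SAP 6.1.3 are redacted after their first line, and SAP 6.1.3.2 and 6.1.3.3 are redacted entirely. The one visible link between an efficacy summary and a set is the abstinence description in SAP 6.2.2, which uses both the PD set and the FAS.

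**The concern.** Time on drug and compliance are known only after randomisation, and either may depend on the arm. Protocol 3.3 explains up-titration as a period for adapting to side effects. Protocol 3.7 lists dizziness, initial insomnia and euphoric mood among the most frequent of these. Protocol 7.2 allows discontinuation for certain CNS events suspected to be drug-related. Exits in the first 14 days could therefore be more common on AFQ056, although the documents give no rates. TRT05 has no such time limit and could act over all 98 days.

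If the exclusions differ between arms and the patients removed differ in cocaine use from those kept, the groups compared are no longer the randomised groups. The sign of the resulting bias cannot be known in advance.

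The as-treated rule is a separate and smaller matter. It departs from the randomised comparison only when a TRT04 error actually occurs.

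**Working it through.** **Inputs from the plan.** SD 32 percentage points for the proportion of use days, and 30 patients per arm (protocol 11.7). The sample size of about 60 cannot be reproduced, because the target effect and decision criterion are not in the visible text. What follows from the visible inputs is the precision:

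SE = 32 × √(2/30) = 8.3 points with all 60 analysed.

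**Assumptions, not document figures.** Share excluded: 20% in one arm (6 of 30) and 10% in the other (3 of 30). Distance d of the excluded patients' mean from the overall mean: 10 to 20 points. No drug effect.

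**Shift from selection.** If a share p is removed and its mean lies d above the overall mean, the retained mean falls by d × p/(1−p). The difference between arms shifts by d × [p₂/(1−p₂) − p₁/(1−p₁)]:

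- Bracket: 0.10/0.90 − 0.20/0.80 = 0.111 − 0.250 = −0.139.
- d = 10: −1.4 points, or 0.17 of the 8.3-point SE.
- d = 20: −2.8 points, or 0.34 SE.
- The sign reverses if d is negative or the arms are swapped.
- Equal p and equal d in both arms: 0.

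**Precision after exclusion (24 and 27 patients).** Retained variance, taking equal variance in excluded and retained patients, is 32² − p × d²/(1−p).

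- d = 10: SDs 31.6 and 31.8; SE = √(31.6²/24 + 31.8²/27) = 8.9 points.
- d = 20: SDs 30.4 and 31.3; SE = √(30.4²/24 + 31.3²/27) = 8.6 points.

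Against these SEs the shifts are 1.4/8.9 = 0.16 and 2.8/8.6 = 0.32 SE, taking unrounded values.

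**Dependence on the assumptions.** If only one arm loses an extra share f, and the gap in mean use between its excluded and retained patients is g, the shift is f × g. With f = 10% and g = 20 points it is 2.0 points; with f = 30% and g = 32 points it is 9.6. Nothing in the documents selects a value in this range.

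**As treated.** Moving one patient, d points from the mean, between arms of 30 leaves 29 and 31. The difference shifts by d × (1/29 + 1/31) = 0.067 × d, which is 0.7 points at d = 10 and 1.3 points at d = 20. No TRT04 frequency is given.

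**Cost of admitting short exposures.** The primary variable is divided by the days up to the last dose, so one use day is worth 100/13 = 7.7 points at 13 days, 100/2 = 50 points at 2 days, and 100 points at 1 day.

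**The case against.** A reader might infer that the primary comparison is run on the PD set. The documents do not support that. The heading of SAP section 6 refers to pharmacodynamic parameters, but it names a type of variable, in parallel with the PK heading of section 5. The FAS is also defined by available PD data. The PD set is the protocol's only efficacy set, but the SAP added a set free of the 14-day and compliance rules, presumably for a purpose. The redacted text may already make the FAS primary or use it for sensitivity. Only *possibly the PD set* can be defended.

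A reader might also infer that compliance is undefined throughout. It is not. The medication-compliance paragraph of the protocol's design section, just before 3.2, defines adherence as tablets taken over tablets scheduled for the treatment phase. Protocol 7.2 has numerical missed-dose limits for discretionary discontinuation. Neither is linked to TRT05, so the cut-off is what is missing. TRT05 does not contradict protocol 11.1, which already excludes deviations with relevant PD impact; only the 14-day rule is new.

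A minimum exposure has a rationale for an on-treatment proportion treated as normal. A one-day exposure can only give 0 or 100%. Entry requires at least 3 abstinent days before Day 1 (protocol 4.1), so very early exits may be measured over an unrepresentative window. This objection stands as a real cost of using the FAS.

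Protocol 10.3 has deviations determined before the treatment codes are released. That limits manipulation but does not restore comparability, because the selecting events still follow randomisation. Replacement of withdrawn patients (protocol 6.3 and 11.7) could restore numbers without removing selection.

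**Conclusion.** The definitional points hold on visible text, whichever set is primary. The two PD-set definitions differ by the 14-day rule, TRT05 has no visible cut-off, and the as-treated rule reaches the efficacy sets, including the FAS.

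Bias from selection is conditional. It needs the PD set to be the primary set, and exclusions that both differ by arm and relate to cocaine use. Under the assumed 20% versus 10% it is 1.4 to 2.8 points, about a sixth to a third of a standard error, in either direction. A claim that the plan favours AFQ056 would go beyond the documents. The as-treated effect is about 0.7 to 1.3 points for each patient moved, at the same assumed distances, and nil if no TRT04 error occurs.

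Using the FAS would reduce selection but not remove it, because the primary variable stops at the last dose (protocol 11.4.1 and 11.4.3; SAP 6.1.1).

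**What to change.** 1. In SAP section 4 and protocol 11.1, limit assignment by treatment received to the safety and PK sets, and analyse efficacy by randomised arm. Align the TRT04 row of Table 4-1.
2. Confirm, or name, the existing FAS as the set for the primary and secondary efficacy comparisons, and report the PD set as supportive. If the redacted text already does this, confirmation is enough.
3. Reconcile the PD-set definitions of protocol 11.1 and SAP section 4, including whether the 14-day rule belongs in both.
4. Tie TRT05 to the protocol's existing adherence formula and write down its cut-off before unblinding.

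The cost is wording: a short protocol edit and a SAP amendment, for which Table 4-1 already provides ("If updates to this table are needed, an amendment to the SAP needs to be implemented prior to DBL"). No patients or data are added. The downside is some dilution of an on-treatment effect, and unstable proportions from patients with very few days on drug. Reporting the PD set alongside shows how far those patients affect the result.
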